6.4.4 Analysis of Exploratory Endpoints

Assessment of the mean change in the frequency and severity of mild, moderate and severe VMS from baseline to each week up to week 12 will be analyzed using the same MMRM model as the primary analyses.

For non-VMS efficacy endpoints Visits are used rather than weeks, as described in Section 6.10.1.1.

Percent reduction, PROMIS (SD and SRI total scores), MENQOL (domain and total scores), and WPAI-VMS domain scores will be assessed using an MMRM model as described in [Section 6.4.1.1 Co-Primary Analysis].

VMS responders will be analyzed as described for the secondary responder endpoints.

PGI-S and PGI-C (SD) and EQ-5D domain scores-will be summarized and analyzed using Cochran Mantel Haenszel (CMH) test with modified ridit scores. PGI-S and EQ-5D will also be adjusted for the baseline score. The mean and standard deviation will also be provided for the EQ-5D domain scores.

The severity calculation excludes mild events at both baseline and post-baseline, using the same model as the primary analyses.

The mean change in the severity of moderate and severe VMS from baseline to each week up to week 12 (both baseline and post-baseline severity include only moderate and severe VMS events in the calculation) will be analyzed using the same MMRM model as the primary analyses.

The median change in serum concentrations of sex hormones and sex hormone-binding globulin (SHBG) from baseline to weeks 4 and 12 will be summarized.

The daily frequency of moderate and severe VMS for the first week will be summarized and graphically displayed by each day.

An exploratory analysis will be conducted using the thresholds for clinical meaningful within subject change from an anchor based analysis.

In order to provide further context for interpretation of change in the frequency of hot flashes, the anchor based analysis will be conducted to empirically define the threshold for meaningful within-subject reduction. A separate Psychometric Analysis Plan (PAP) [RTI Health Solutions] will provide the detailed description of the psychometric analytic methods to be used in determining the clinically meaningful within-subject reductions at week 4 and week 12. The thresholds will be estimated according to the prespecified PAP.

A subject will be classified as a responder if her change from baseline to Week 4 is equal or larger than the threshold at Week 4. Similarly, a subject will be classified as a responder if her change from baseline to Week 12 is equal or larger than the threshold at Week 12.

A logistic regression analysis will be conducted to compare each dose of fezolinetant to placebo. The logistic regression model will include the treatment group and smoking status (current vs. former/never) as factors, and baseline mean frequency of vasomotor symptoms as a covariate. Missing data will be imputed by considering the following approaches: (1) last-observation-carried-forward (primary), (2) missing as a non-responder, and (3) including observed cases only. Odds ratio (fezolinetant over placebo), its 2-sided 95% CI and nominal p-value will be presented.

This analysis will be conducted using the thresholds that are calculated from the pooled studies (ASP2693-CL-0301 and ASP2693-CL-0302) in the Integrated Summary of Efficacy

(ISE). An additional analysis will be conducted using the thresholds that are calculated from each study to further characterize the study results.

6.5 Analysis of Safety

All analysis of safety will be presented by treatment group for SAF, unless specified otherwise. For analyses by visit, the visit windows from Section 6.10.1.2 will be applied. Except for adverse events and follow-up visit data, only data up to one day after the last dose date will be considered for the analyses.

The baseline value for safety endpoint will be the last non-missing value taken on or prior to first dose of study drug unless otherwise noted.

6.5.1 Adverse Events

Per protocol, a TEAE is defined as an AE observed after starting administration of the study drug and up to 21 days after the last dose of the study drug.

A TEAE during the DB period, is defined as an AE observed after starting administration of the study drug and up to 21 days after the last dose of the double-blind study drug, and before the first dose of treatment for extension phase for subjects who entered extension treatment period.

A study drug-related TEAE is defined as any TEAE with a causal relationship of YES by the investigator.

The sponsor has a list of events that they classify as "always serious" events. If an AE is reported that is considered by the sponsor to be an SAE per this classification as "always serious", the AE will be treated as an SAE in tables and listings, and flagged as 'always serious' in AE listings.

An overview table will include the following

- Number of TEAEs,
- Number and percentage of subjects with TEAEs,
- Number of drug related TEAEs,
- Number and percentage of subjects with drug related TEAEs,
- Number of serious TEAEs,
- Number and percentage of subjects with serious TEAEs,
- Number of serious drug related TEAEs,
- Number and percentage of subjects with serious drug related TEAEs,
- Number of TEAEs leading to permanent discontinuation of study drug,
- Number and percentage of subjects with TEAEs leading to permanent discontinuation of study drug, and
- Number of deaths.

The number and percentage of subjects with TEAEs in the following AE categories will be summarized by system organ class (SOC), high level term (HLT) and preferred term (PT):

- TEAEs,
- Drug-related TEAEs.

The number and percentage of subjects with TEAEs in the following AE categories will be summarized by SOC and PT:

- Serious TEAEs,
- Drug-related serious TEAEs,
- TEAEs leading to permanent discontinuation of study drug,
- Drug-related TEAEs leading to permanent discontinuation of study drug,
- TEAEs that equal to or exceed a threshold of 5% in any treatment group (threshold is based on PT),
- TEAEs excluding serious adverse events that equal to or exceed a threshold of 5.0% in any treatment group.

The number and percentage of subjects with TEAEs, as classified by PT only, will be summarized for each treatment group.

The number of TEAEs and the number and percentage of subjects with TEAEs, as classified by SOC and PT will be summarized by severity and by relationship to study drug. In the subject count, if a subject has multiple TEAEs with the same SOC or PT, but with differing severity or relationship, then the subject will be counted once with the worst severity and highest degree of relationship. If severity or relationship is missing for all episodes of the event, the subject will be counted under missing severity or relationship. In the adverse event count, the adverse events will be presented in each category they were classified to. Drug related TEAEs will be presented in a similar way by severity only.

Following adverse events of special interest are defined:

- Adverse event of uterine bleeding
- Endometrial hyperplasia, cancer, or disordered proliferative endometrium
- Adverse event of thrombocytopenia
- Adverse event of liver test elevations
- Adverse event of bone fractures
- Adverse events of abuse liability
- Adverse events of depression
- Adverse events of wakefulness
- Adverse events of effect on memory

Search terms defining the AESIs will be pre-specified and separately documented.

The number and percentage of subjects with AESIs, as classified by PT will be separately summarized for each treatment group and listings of these adverse events will be provided.

The number and percentage of subjects with TEAEs associated with COVID-19, as classified by SOC and PT, will be summarized for each treatment group and overall.

6.5.2 Clinical Laboratory Evaluation

Quantitative values evaluated by the central laboratory including hematology, biochemistry, and urinalysis will be summarized using mean, standard deviation, minimum, maximum and median by treatment group at each analysis visit. Additionally, a within-subject change will be calculated as the post-baseline measurement minus the baseline measurement and summarized in the same way. Each laboratory result will be classified as low (L), normal (N), or high (H) at each visit according to the laboratory supplied reference ranges.

The number and percentage of subjects below and above reference range will be summarized for each treatment group at each visit.

Number and percentage of subjects with platelets $< 150000/uL (150 \ 10^9/L)$ will also be summarized.

Frequency tabulations of qualitative clinical laboratory variables (urinalysis) will be presented for each treatment group at each visit.

For hematology and biochemistry shift tables will be presented for each treatment group:

• Summary shifts of reference range changes from baseline to worst finding during the treatment period (shift from normal or high to low, shift from normal or low to high, categorized increase [shift from low to normal or from normal to high], categorized no change [value stays in the same reference range], categorized decrease [shift from high to normal or from normal to low]).

For hormone related parameters, if the value is below the low limit of quantification, the value will be imputed as half of the LLOQ. In addition, the percentage of subjects who have BLOQ values at baseline who then have measurable post-baseline values will be summarized.

6.5.2.1 Liver Safety Assessment

The liver safety assessments will be summarized by the categories below based on the measurements from Alkaline Phosphatase (ALP), Alanine Transaminase (ALT), total bilirubin, Aspartate Transaminase (AST) and their combination. These parameters will be based on measurements from a central laboratory.

The subject's highest value during the double-blind investigational period (from day of first dose of study drug until first dose of double-blind treatment period) will be used.

- ALT > 3xULN, > 5xULN, > 8xULN, > 10xULN, >20xULN
- AST > 3xULN, > 5xULN, > 8xULN, > 10xULN, > 20xULN
- ALT or AST > 3xULN, > 5xULN, > 8xULN, > 10xULN, >20xULN
- ALP > 1.5 xULN
- Total Bilirubin >2xULN
- (ALT or AST > 3xULN) and Total Bilirubin > 2xULN
- (ALT or AST > 3xULN) and ALP< 2xULN and Total Bilirubin > 2xULN

The last 2 criteria where 2 or more parameters are evaluated will be with the measurements on the same day or up to 1 day apart. The denominator for each criterion will be the number of subjects who have at least one value during the double-blind period. The number and percentage of subjects meeting the criteria during the double-blind period will be summarized by treatment group.

Due to COVID-19, patients might not be able to visit the clinical site and have clinical laboratory tests taken at the clinical site and evaluated by the central laboratory, in this case clinical laboratory tests can be taken by a local laboratory. The liver biochemistry safety assessments will be summarized including central and locally collected laboratory data due to COVID-19. This analysis is considered the primary analysis for the liver safety assessments.

The secondary analysis for liver biochemistry will be repeated by the data evaluated by the central laboratory but excluding the data that are impacted by COVID-19, which include the data recorded after the subjects were diagnosed of COVID-19, after study drug discontinuation due to COVID-19, during dose interruption due to COVID-19, and visits that are out of protocol window or data collected via home visits due to COVID-19 recorded in the eCRF.

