I. LIST OF ABBREVIATIONS AND KEY TERMS

List of Abbreviations

| Abbreviations | Description of abbreviations |
|---------------|-------------------------------------|
| ANCOVA | Analysis of Covariance |
| ASCM | Analysis Set Classification Meeting |
| ATE | Active Treatment Extension |
| CI | Confidence Intervals |
| СМН | Cochran Mantel Haenszel |
| COVID-19 | Coronavirus Disease 2019 |
| FAS | Full Analysis Set |
| GCP | Good Clinical Practice |
| ISE | Integrated Summary of Efficacy |
| MAR | Missing at Random |
| MMRM | Mixed Model Repeated Measures |
| PAP | Psychometric Analysis Plan |
| PKAS | Pharmacokinetics Analysis Set |
| PPS | Per-Protocol Analysis Set |
| SAF | Safety Analysis Set |
| SAP | Statistical Analysis Plan |
| SD | Standard Deviation |
| TLF | Tables, Listings and Figures |
| VMS | Vasomotor Symptoms |

List of Key Terms

| Terms | Definition of terms |
|--------------------------------------|--|
| Double-blind Treatment Period | The 12 weeks of treatment after the first administration of study drug and prior to first administration of study drug in the active treatment extension period. Only this period contains a placebo treatment. |
| Active Treatment Extension Period | Period of time after the first administration of study drug in the active treatment extension period after completing 12 weeks of placebo- controlled double-blind treatment until the last dose of the study drug (at Week 52 or early discontinuation). |
| Follow-up Period | Period of time after the last dose of study drug or last assessment of the protocol. Additional safety data and follow-up observations for sustained adverse events are conducted during this period. |

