1 INTRODUCTION

This Statistical Analysis Plan (SAP) contains technical and detailed elaboration of the principal features of the analysis described in the protocol, and includes procedures for executing the statistical analysis to fulfil the objectives of the study.

The analyses described in the SAP will be conducted after all subjects complete the double-blind treatment period at 12 weeks. Only data pertaining to the double-blind treatment period (all data for subjects early discontinued during the double-blind period, or data from 12-week double-blind period prior to first dose of study drug in the active treatment extension period for subjects entered the extension period) will be used. A separate SAP will describe the analysis of the 52-week study data period, including the active treatment extension period.

This SAP will be approved prior to the database lock for the 12-week double-blind period.

Changes from the planned analyses in the finalized SAP that impact the statistical analyses will be documented and justified in the Clinical Study Report (CSR).

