6.10 Additional Conventions

6.10.1 Analysis Windows

Study Day for analysis windows during the double-blind treatment phase will be calculated as date of visit/assessment – first dose date +1.

Study Day for the follow-up phase will be calculated as date of visit/assessment – last dose date of double-blind treatment.

As noted in Section 1 only data pertaining to the double-blind treatment phase will be used in the 12-week treatment phase analysis:

- The active treatment extension period data (beginning from the second day of the active treatment extension period) will be excluded, assuming the Week 12 assessments are done before the first dose of active treatment extension period.
- Follow-up data that also falls into the active treatment extension period will be excluded (i.e., early discontinuations within the active treatment extension period phase).

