6.10.1.2 Safety Analysis Windows

Except for adverse events, for the analysis window (weeks prior to the follow-up period), data within 1 day after the last day of exposure to double-blind treatment will be included.

The end of overall treatment is defined as the last day of treatment (e.g., discontinued study or entered follow-up period) +1 and the follow-up period begins at last overall treatment + 2 days and onward.

The data summary by visits will be done following the analysis windows specified in the table below:

| Analysis | Scheduled Day in Protocol | Analysis Windows (day) | | |
|----------------------------|---|---|----------|----------|
| Visits | | a) | b) | c) |
| Baseline | Day 1 | Last non-missing value on or priot to day 1 (inclusive) | | |
| Week 2 | Day 15 | 2 to 22 | | |
| Week 4 | Day 29 | 23 to 43 | 2 to 43 | 2 to 57 |
| Week 8 | Day 57 | 44 to 71 | 44 to 71 | |
| Week 12* | Day 85 | 72 to 92 | 72 to 92 | 58 to 92 |
| Extension Period Visits | Beginning on day of first dose of extension period treatment | Defined in extension period SAP | | |

a) Apply to liver biochemistry and INR testing

- b) Apply to complete Clinical laboratory and urinalysis, Vital signs
- c) Apply to Blood PD/PK sample

*The analysis window for the Week 12 ECG assessment (Target Day 85) is Day 2 through Day 92

If more than one observation exists within the analysis window, the same rules will be followed as described above for efficacy analysis visit windows, except that if there are two observations that have the same distance from the scheduled day, the value that is after the scheduled day will be selected in the analysis.

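### 12-week SAP 6.5.2.1 closes the peak liver value window at the dose that opens it, so the definition as written admits no post-dose result

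*SAP*

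**What the plan says.** 12-week SAP 6.5.2.1 (Liver Safety Assessment) uses each woman's highest value in the double-blind investigational period. It defines that period in parentheses as "from day of first dose of study drug until first dose of double-blind treatment period". The values feed counts of ALT, AST, ALP and total bilirubin above stated multiples of ULN, and two combined ALT/AST-bilirubin criteria. The section plans a primary version (central plus COVID-related local laboratory data) and a secondary version (central data, excluding COVID-affected results).

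Five other places bear on the window:

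- **List of Key Terms, 12-week SAP:** the double-blind period is the 12-week span "after the first administration of study drug and prior to first administration of study drug in the active treatment extension period".
- **Same section 6.5.2.1, denominator:** "The denominator for each criterion will be the number of subjects who have at least one value during the double-blind period".
- **12-week SAP 6.5:** apart from adverse events and follow-up visit data, "only data up to one day after the last dose date will be considered for the analyses". Section 6.10.1.2 agrees: "data within 1 day after the last day of exposure to double-blind treatment will be included".
- **Protocol 7.5.2:** the highest value is taken over the treatment period.
- **52-week SAP 6.5.2.1:** the matching sentence opens at the first fezolinetant dose and ends at the last extension dose + 1 day.

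**The concern.** The first dose of study drug is also the first dose of the double-blind period. The parenthesis therefore describes a window with no treatment time in it, and it disagrees with the table's own denominator.

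The table matters. Protocol 1.5 classes liver injury as an important potential risk, on the basis of phase 2b transaminase cases. It reports elevations in 7 subjects between 4 and 8 weeks after starting treatment, which is inside the time this phrase shuts out. Only the double-blind period contains placebo. The 52-week liver table starts at the first fezolinetant dose, so it holds no results from women while on placebo. The 12-week SAP's liver adverse events of special interest (6.5.1) and its by-visit summaries, reference-range counts and shift tables (6.5.2) do not use the phrase. They do not give xULN categories or combined criteria either.

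**Working it through.** The plan states no figure for this point, so there is none to reproduce. The check is date arithmetic on the SAP's own days.

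**Inputs**

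- Study Day = assessment date − first dose date + 1 (12-week SAP 6.10.1), so the first dose is on Day 1.
- Scheduled post-dose liver draws: Days 15, 29, 57 and 85, each ± 3 days (Protocol Table 1; footnote k limits visit 2b at Week 2 to liver biochemistry and INR).
- Liver analysis windows: Days 2–22, 23–43, 44–71 and 72–92 (12-week SAP 6.10.1.2, column a).
- On visit days blood is drawn before the dose (Protocol 5.1.1). The last value on or before Day 1 is baseline (12-week SAP 6.10.1.2).
- Assumption: the first extension dose is taken at the Week 12 visit and the last double-blind dose the day before.

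**Step 1: the window as written.** It opens on Day 1 and closes on Day 1, so its length is 1 − 1 + 1 = 1 day. The earliest scheduled draw is Day 15 and the earliest analysis window opens on Day 2. Draws admitted: 0 of 4. Analysis windows overlapped: 0 of 4.

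**Step 2: what Day 1 can contribute.** The scheduled Day 1 sample is predose and is a baseline value. Exclusion criterion 11 allows entry with ALT or AST up to 1.5 × ULN, so cells for more than 3 × ULN would be at or near zero in every arm.

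**Step 3: candidate corrections.**

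| Week 12 visit | Last double-blind dose | Draws admitted, ending at last dose | Draws admitted, ending at last dose + 1 day |
|---|---|---|---|
| Day 82 | Day 81 | 3 of 4 | 4 of 4 (window to Day 82) |
| Day 85 | Day 84 | 3 of 4 | 4 of 4 (window to Day 85) |
| Day 88 | Day 87 | 3 of 4 | 4 of 4 (window to Day 88) |

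Swapping the word first for last is therefore not enough under this assumption. The + 1 day decides whether the Week 12 draw counts.

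**Step 4: which text is the outlier.** The words just before the parenthesis, the denominator and count sentences of 6.5.2.1, and Protocol 7.5.2 all describe the whole period. Sections 6.5 and 6.10.1.2 and the 52-week sentence supply an end at last dose + 1 day. Only the parenthesis points elsewhere.

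**The case against.** The strongest reply is that this is a slip of the pen. The sentence itself names the double-blind investigational period, and the denominator, Protocol 7.5.2 and the general safety rules all agree on it. A programmer would have to ignore every one of them to produce an empty table. Individual stopping rules, the DMC and the liver panel do not depend on the phrase, so no woman's protection is affected. All of that stands, and it limits the size of the point. It does not make the phrase correct. Section 6.5.2.1 is listed as revised in both SAP 7.1 and 7.2, and the words are still there. Knowing the intended period also does not by itself fix the end date, as Step 3 shows.

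A reader might infer two further contradictions. The documents do not support either as a separate error.

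- **Women who stop early.** The 12-week SAP Introduction includes "all data for subjects early discontinued during the double-blind period", which looks wider than last dose + 1 day. The Introduction only states which data belong to the 12-week analysis. Sections 6.5 and 6.10.1.2 are the specific safety rules within it, and 6.5 exempts follow-up visit data from its cut-off.
- **The day of the first extension dose.** Section 6.10.1 excludes extension data "beginning from the second day of the active treatment extension period", while the 6.10.1.2 table has extension visits "Beginning on day of first dose of extension period treatment". The second phrase sits in the scheduled-day column for extension visits; it does not remove predose Week 12 samples. Section 6.10.1 assumes that Week 12 assessments precede the first extension dose, and Protocol 5.1.1 draws blood before dosing.

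**Conclusion.** The point holds as an error in an operative definition. As written, the window admits 0 of 4 scheduled post-dose draws to the only placebo-controlled xULN and combined-criteria table, in both its versions, and it contradicts the surrounding rules. The 0 of 4 rests on the literal text and the SAP's own definition of the double-blind period. The 3 of 4 versus 4 of 4 comparison rests on the assumption about the last double-blind dose given in the working.

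The likely practical effect is small, because the intent can be recovered from the same section and from 6.5 and 6.10.1.2.

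A reader might infer that the table will be empty, or that the on-drug liver signal would be lost. The documents support neither. An empty table would require ignoring several agreeing passages. Even under a literal coding, the 52-week table would still categorize the active arms' results from their first dose. What would be lost is the placebo column and the side-by-side comparison.

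**What to change.** In 12-week SAP 6.5.2.1, replace the parenthesis with: *day of first study drug dose through last double-blind dose + 1 day, and before the first extension dose; Week 12 samples drawn predose on the day of the first extension dose are included*. This follows 6.5, 6.10.1 and 6.10.1.2 and applies to both the primary and the secondary version of the table.

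The cost is one phrase, with no new data, table or analysis. There is one small consequence to state in the text. Apart from those Week 12 predose samples, liver values taken more than 1 day after the last double-blind dose stay out of this on-treatment table. They are reported with the follow-up visit data, as 6.5 allows.
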